This project will utilize sensitive, early biomarkers of disease risk, including whole-body adiposity, hepatic triglyceride content and carotid IMT, directly relevant to diabetes and cardiovascular disease risk, respectively. **The overall aim of this two-study research plan is to characterize risk using these sensitive biomarkers in children with mental health disorders, and evaluate the magnitude of change observed in these biomarkers in children receiving an established weekly behavioral weight-loss (BWL) intervention.** This will be accomplished with a randomized, controlled test of the effects of a 16-week behavioral weight loss intervention on CTGC, PDFF and IMT in overweight/obese antipsychotic (AP)-treated children randomized 2:1 to weekly BWL treatment or monthly diet and exercise education or usual care (UC), versus nonpsychiatric (NP) overweight or obese children undergoing the weekly BWL treatment.

Study Aims for this pilot randomized controlled trial:

Aim 1: To evaluate the main effect of time of 16 weeks of a BWL intervention on DEXA-measured whole body adiposity in overweight/obese antipsychotic (AP)-treated children compared to nonpsychiatric (NP) overweight or obese healthy controls, and in AP-treated youth randomized to monthly Usual Care (UC).

Aim 2: To evaluate the main effect of time of 16 weeks of a BWL intervention on PDFF in overweight/obese AP-treated children compared to NP overweight or obese healthy controls, and in AP-treated youth randomized monthly UC.

Aim 3: To evaluate the main effect of time of 16 weeks of a weekly behavioral weight loss intervention on CIMT in overweight/obese AP-treated children compared to NP overweight or obese healthy controls, and in AP-treated youth randomized monthly UC.

Primary Hypothesis: *Change in DEXA-measured total fat and PDFF/IMT will be more pronounced in the weekly weight loss intervention groups compared to the monthly Usual Care intervention.*

Exploratory Aims:

a) To evaluate the effects of 16 weeks' of weekly versus monthly weight loss intervention on changes in standard cardiometabolic risk factors (e.g., fasting lipids, insulin, glucose, adiponectin, fibrinogen, high sensitivity C-reactive protein and very low density lipoprotein particle size).

b) To evaluate baseline psychiatric symptom severity on treatment adherence and changes in biomarkers during treatment.

PARTICIPANT RECRUITMENT & SELECTION

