Previously published carotid IMT numbers indicating significant differences between obese children with and without metabolic syndrome criteria provide a crude proxy for the difference between an active intervention group and UC, suggesting that we should be able to detect a difference of 1.27 +/- 0.005 in intima media stiffness (units are logarithmically transformed and are therefore unitless).¹⁰ Power to detect differences in CIMT between the 3 treatment groups using a sample size of 20 per group, an alpha of 0.05, and an effect size of 0.16 was calculated to be 0.17.

Previous reports of hepatic triglyceride content in the general population indicate that 33.6% of the population meet criteria for hepatic steatosis (> 95th percentile of hepatic triglyceride content of 5.56%, corresponding to 55.6 mg/g) based on weight criteria, with obese patients being more likely to meet criteria for steatosis than healthy controls.³⁵ Power to detect differences in Hepatic Triglyceride Content between the 3 treatment groups using a sample size of 20 per group, an alpha of 0.05, and an effect size of 0.49 was calculated to be 0.92.

DEXA power calculations were based on previously noted weight loss of up to 8-10% in other studies of behavioral weight loss interventions between 2 and 5 months in length with known SDs on the observed mean change.^{36,37} Based on our previous experience with antipsychotic treated and untreated children, we anticipated that the baseline DEXA % fat would be 14-15 kg of body fat, or roughly 30-40% body fat. Anticipating up to a 5% loss from baseline fat measured by DEXA, less than the 8-10% observed in other studies, due to potential effects of the ongoing mental health condition and the antipsychotic treatment in this sample, we estimated a difference between active treatment groups (AP-treated vs. NP) of 2 +/-3 kg loss from a baseline of 15 kg total fat. Power to detect differences in DEXA Total Fat between the 3 treatment groups using a sample size of 20 per group, an alpha of 0.05, and an effect size of 0.53 was calculated to be 0.96.

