Analytic approach: the primary goal was to compare changes over time in the three risk factors (CIMT/DEXA/PDDF) among three groups: obese AP-treated children randomized to the weekly intervention, obese NP children also receiving weekly behavioral weight loss treatment, and an obese usual care (UC) reference group. Comparisons of interest were between each of the two active treatment groups and UC, as well as between the two active intervention groups themselves (AP-treated vs. NP). Because this is a pre-post design with data collected only at baseline and at 16 weeks, our analytic strategy used an analysis of covariance (ANCOVA), in which the 16-week value of the risk factor is the dependent variable and the predictors are the baseline value of the risk factor and the study group (three level factor), with contrasts of interest listed above. Other analyses performed adjusted for covariates such gender and age to determine whether baseline-adjusted between group differences at 16 weeks can be explained by such covariates. Because of the relatively small sample size in this study, we performed separate analyses of covariance that include precisely one additional covariate, in addition to the baseline value of the risk factor of interest in each analysis.

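### Usual care was given only to antipsychotic-treated children, so neither planned contrast involving the non-psychiatric group isolates an effect of the weight-loss programme

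*Combined protocol and SAP*

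**What the plan says.** The overview in Appendix I, Specific Aims, describes "antipsychotic (AP)-treated children randomized 2:1 to weekly BWL treatment or monthly diet and exercise education or usual care (UC"), set "versus nonpsychiatric (NP) overweight or obese children undergoing the weekly BWL treatment". Aim 1 names the usual-care population outright: "and in AP-treated youth randomized to monthly Usual Care (UC"). Aims 2 and 3 follow the same pattern, and Table 2 in Appendix II has three groups only: AP-BWI, AP-UC and NP-BWI.

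The Analytic approach is less explicit. It calls the third group "and an obese usual care (UC) reference group" without saying that it is AP-only, and the Power paragraph is equally general. Both list the same contrasts: "Comparisons of interest were between each of the two active treatment groups and UC", and then "as well as between the two active intervention groups themselves (AP-treated vs. NP"). The model is an ANCOVA of the 16-week value in which "the predictors are the baseline value of the risk factor and the study group (three level factor"); gender, age and similar covariates are added one at a time.

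The Primary Hypothesis sets the weekly groups, in the plural, against monthly UC. In the DEXA power text, the loss is expected to be smaller than in other studies "due to potential effects of the ongoing mental health condition and the antipsychotic treatment in this sample".

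**The concern.** The effect of BWL in a population is the change under BWL minus the change the same population would show under usual care. AP children have that reference. NP children do not: of the four combinations of population and treatment, one is empty. Two of the three planned contrasts then have no clean meaning as treatment effects.

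- AP-weekly versus NP-weekly is the difference in response plus the difference in course under usual care.
- NP-weekly versus UC compares different children on different treatments.

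Different background courses are foreseeable. The Specific Aims report that 12 weeks of initial antipsychotic treatment increases adiposity. Eligibility asks for about 6 months of prior treatment, so that statement does not give the size here.

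Two conclusions are at stake: that BWL works differently in AP and NP children, and that weekly BWL is effective because NP-weekly did better than UC. No section warns against either or labels the NP contrasts as descriptive.

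**Working it through.** **1. The plan's own figure.** For DEXA total fat the plan states power 0.96 with 20 per group, alpha 0.05 and effect size 0.53. A three-group F test with noncentrality 0.53² × 60 = 16.85 on 2 and 57 df gives 0.956, so the figure reproduces. It concerns detecting any difference among the three groups. A larger sample would estimate a mixed quantity more precisely but would not separate its parts.

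**2. Decomposition.** Let b be the unobserved mean change of NP children under usual care.

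- AP-weekly − NP-weekly = [(AP-weekly − AP-UC) − (NP-weekly − b)] + [AP-UC − b]
- NP-weekly − UC = [NP-weekly − b] + [b − AP-UC]

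In each line the first bracket concerns response to BWL and the second concerns background course. The ANCOVA adjusts for where children start and for one further characteristic. It contains no information on b.

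**3. Illustration in fat mass.** Table 2 gives no DEXA total fat, so I take weight change minus lean change from the group means, ignoring bone and reading lean as kg.

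| Group | Weight change | Lean change | Derived fat change |
|---|---|---|---|
| AP-weekly | −0.12 | +0.78 | −0.90 kg |
| AP-UC | +2.42 | +1.56 | +0.86 kg |
| NP-weekly | −2.30 | +0.59 | −2.89 kg |

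As a cross-check, mean weight × mean percent fat in AP-UC gives 68.56 × 0.4577 = 31.38 and 70.98 × 0.4548 = 32.28, a change of +0.90 kg.

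- Raw AP − NP: −0.90 + 2.89 = 1.99 kg
- BWL effect in AP (randomised): −0.90 − 0.86 = −1.76 kg
- Raw NP-weekly − UC: −2.89 − 0.86 = −3.75 kg
- Difference in response, AP − NP: −1.76 − (−2.89 − b) = 1.13 + b
- Difference in course: 0.86 − b

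With b = 0 (an assumption), 0.86 of the 1.99 kg (43%) is background and 1.13 kg is response; of the 3.75 kg, 2.89 kg is the BWL effect in NP. With b = 0.86 (also an assumption), the background share is nil and the full 1.99 and 3.75 kg are response. The documents give no value for b.

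**4. How many children lie behind the UC figure.** Partial eta² for time is t²/(t² + n − 1). For UC weight, t = 2.42/(2.36/√n), and n = 6 gives 0.558 against the printed 0.56. UC cholesterol means of 168.67 and 150.83 equal 1012/6 and 905/6. Completers of 15, 6 and 17 total 38, which fits 34 error df with three groups and one covariate. Table 1 prints 17 for AP monthly, but 19 + 17 + 21 = 57, not the stated 47. With 7, the combined mean weight is (19 × 77.08 + 7 × 72.37 + 21 × 85.76)/47 = 80.26, as printed; with 17 it is 78.87.

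**5. Precision, with n = 6.** The UC weight change of +2.42 kg has a 95% CI of about −0.06 to +4.90. For derived fat, the SD depends on the unknown correlation of weight and lean changes. It lies between 2.36 − 1.00 = 1.36 and 2.36 + 1.00 = 3.36. The 95% half-width is 2.571 × SD/√6, that is 1.43 to 3.53. So +0.86 kg has at best an interval of −0.57 to +2.29 and at worst −2.67 to +4.39.

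**The case against.** The strongest reply is that the plan never claims differential efficacy. The Aims speak of a main effect of time, the Analytic approach of comparing changes and baseline-adjusted differences, and the study is a feasibility pilot. The power sentence about illness and medication explains why less loss is expected than in other studies, and background gain is as natural a reading of it as weaker response. This stands as far as AP versus NP goes: the contrast is a legitimate description. It does not cover NP-weekly versus UC, which the Primary Hypothesis uses as evidence for weekly BWL.

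Two stronger readings are tempting, and the documents support neither.

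- **A reader might infer that the UC gain of +2.42 kg exceeds the 2 kg the plan expects.** The 2.42 kg is body weight in one arm; the 2 kg is an AP–NP difference in DEXA fat. The like-for-like UC change is about +0.86 kg.
- **A reader might infer that BWL works as well or better in AP children.** The two effects are equal at b = NP-weekly − (AP-weekly − AP-UC). For weight this is −2.30 + 2.54 = +0.24 kg, between 0 and the UC value of +2.42. On the other scales it falls outside that range: BMI z −0.16 + 0.10 = −0.06 (UC −0.03), percent overweight −8.48 + 5.14 = −3.34 (UC +0.04), percent fat −2.47 + 1.13 = −1.34 (UC −0.29), derived fat −2.89 + 1.76 = −1.13 kg (UC +0.86). Body weight is not one of the plan's three risk factors. Its turning point is also very imprecise: SE √(4.29²/17 + 3.04²/15 + 2.36²/6) = 1.62, 95% CI about −3.1 to +3.6 kg.

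**Conclusion.** The point holds as a limit on interpretation. The design identifies one effect of BWL, in AP children, from AP-weekly versus UC. Whether response differs between AP and NP children, and whether BWL works in NP children, cannot be learned from these three groups under the planned ANCOVA. That follows from the design and needs no numbers.

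The size is illustrative: about 0.86 of a 1.99 kg raw fat difference would be background if NP children did not change under usual care. It rests on group means, neglect of bone, inferred completer numbers and an assumed b. NP height rose 0.01 m, so these children were growing and zero change cannot be taken for granted. PDFF and CIMT have the same structure, but Table 2 gives no changes for them.

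**What to change.** - In the Study Aims and Primary Hypothesis, the Power paragraph and the Analytic approach, state that UC consists only of AP-treated children.
- Take the effect of BWL, and the test of the Primary Hypothesis, only from the randomised AP-weekly versus UC contrast.
- Label AP-weekly versus NP-weekly and NP-weekly versus UC as non-randomised, descriptive differences in 16-week course. Draw no conclusion from them about differential efficacy or about efficacy in NP children.
- Optionally, print the NP change under usual care at which the two BWL effects would be equal. Give its confidence interval and call it a change under usual care, not untreated, since UC includes monthly education.

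The cost is wording; no new patients are needed. The conclusion becomes narrower and rests on the smaller randomised comparison, about 15 versus 6 inferred completers. For weight that comparison gives −0.12 − 2.42 = −2.54 kg. With pooled SD √[(14 × 3.04² + 5 × 2.36²)/19] = 2.88, the 95% CI is −5.45 to 0.37.

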Inclusion Criteria: **i)** 6-18 years old (at any point during study participation); **ii)** BMI percentile \geq 85 **iii)** Meet DSM-IV criteria for one or more childhood onset psychiatric disorders including disruptive behavior disorders (attention deficit disorder, conduct disorder, oppositional defiant disorder and disruptive behavior disorder not otherwise specified), affective disorders (bipolar affective disorder, major depressive disorder and mood disorder not otherwise specified), anxiety disorders (generalized anxiety disorder, obsessive compulsive disorder, separation anxiety, social and other specific phobias) as well as other disorders, including autism spectrum disorders (autistic disorder, Asperger's Syndrome and pervasive developmental disorder not otherwise specified), psychotic disorders (schizophreniform disorder, schizophrenia and psychotic disorder not otherwise specified) and movement disorders (tic disorder, Tourette's Syndrome) (*EXCEPT* for the Obese or Overweight Control Group, none of whom can meet criteria for any DSM-IV Axis I psychiatric illness); **iv)** Participants treated with psychotropic medication may not have any medication changes for 1 month prior to study enrollment at the discretion of the PI, and Antipsychotic-Treated Participants must be treated with an antipsychotic \geq approximately 6 months with no antipsychotic medication dose changes for 1 month; **vi)** The Healthy Overweight or Obese Control Group may not be currently taking any prescription medications (multivitamins, over the counter medications, glucocorticoid nasal spray and inhalers are permitted, as well as non-sedating antihistamines such as but not limited to Claritin (loratadine) and Zyrtec (cetirizine)); and **vii)** Participants between 6-17 years old able to give assent and have a parent/guardian that can provide written informed consent, and 18 year-old participants will be able to provide written informed consent.

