Hepatic ¹H Magnetic Resonance Spectroscopy (MRS)-estimated proton density fat fraction (PDFF): 1.5T Siemens Magnetom Vision scanner (Siemens, Erlanger, Germany) were conducted to quantify hepatic triglyceride content.²⁴ Participants were placed in a supine position the scanner using standard array coils. Hepatic triglyceride content was determined within a voxel size of 15 × 15 × 20 mm³ by using a point resolved spectroscopy (PRESS) single-voxel technique. Data were averaged from 20 scans and obtained with a repetition time of 2 seconds. Spectra were acquired at echo times of 24, 30, 35, 40, 50 ms at upper left lobe and mid to lower lobe voxels and at an echo time of 24 ms at the mid-lobe voxel to estimate and correct for the T2 decay of the signals. Images were corrected for relaxation and analyzed using jMRUI, a Java-based graphical user interface quantification package that allows time-domain analysis of *in vivo* MR data.²⁵ All frequencies, i.e., chemical shifts, were measured relative to the principal water ¹H resonance, which is referenced as zero Hz.

Dual Energy X-ray Absorptiometry (DEXA): to assess Percent total body fat and percent total fat-free mass (Hologic QDR 1000/w, Waltham, MA).²⁶ Appendicular skeletal muscle mass will be estimated from these data as described and validated by Heymsfield et al.²⁷ In addition, changes in bone mineral density (BMD) will be calculated for the exploratory aim. The error of regional fat free mass determination by this technique, as compared with computerized tomography, is less than 5%.^{26,27}

9-13-MHZ B-mode Carotid Ultrasound: (Vivid E9, GE Medical Systems using automatic edge detection software) for the measurement of carotid intima media thickness (IMT) in the longitudinal and cross-sectional axes. IMT was expressed as the average minimum, mean and maximum thickness measured over a 1 cm region of the bilateral posterior common carotid walls approximately 1-2 cm proximal to the carotid bulb. Studies will be reviewed and analyzed by two independent readers, who will be blinded to subject data. The intra- and inter-observer intraclass correlation coefficients for IMT measurements at our laboratory are 0.91 and 0.88, respectively.²⁸

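### The two contrasts with the non-randomised NP group rest on baseline-adjusted ANCOVA alone, which does not estimate the stated target (difference in change) when groups start apart and the baseline slope is below 1

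*Combined protocol and SAP*

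**What the plan says.** Under Data Management, Safety & Adverse Event Reporting, the Analytic approach paragraph gives the aim: "the primary goal was to compare changes over time in the three risk factors (CIMT/DEXA/PDDF) among three groups". The model is a single ANCOVA in which "the 16-week value of the risk factor is the dependent variable and the predictors are the baseline value of the risk factor", together with a three-level group factor. It serves every contrast: "Comparisons of interest were between each of the two active treatment groups and UC, as well as between the two active intervention groups themselves". The only further adjustment adds one covariate at a time, such as gender or age. No analysis of change scores is planned.

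Specific Aims makes clear that randomisation (2:1, weekly treatment or UC) applies to the AP youth only. The third group is set beside them, "versus nonpsychiatric (NP) overweight or obese children undergoing the weekly BWL treatment". The Inclusion Criteria say of these controls: "none of whom can meet criteria for any DSM-IV Axis I psychiatric illness". AP-weekly vs UC is therefore a randomised contrast; AP-weekly vs NP and NP vs UC are not.

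Appendix II, Table 2 labels its group test as time by treatment. Its error degrees of freedom (34 in most rows, 33 for the Aberrant Behavior Checklist) and most of its F values are those of the ANCOVA.

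**The concern.** In a randomised contrast the expected baseline gap is zero, so ANCOVA and change scores have the same target. Where the groups come from different populations the two targets separate (Lord's paradox). If the within-group slope of week 16 on baseline is below 1, ANCOVA expects each group to move toward a common mean. Two groups that stay exactly where they were then appear to differ at week 16.

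Eligibility makes a gap on behavioural measures certain, and Table 1 shows sizeable gaps on two of the three risk factors. At stake is whether a reported difference between AP and NP children, or between NP children and UC, reflects a different response to treatment or only who was recruited. A column labelled as time by treatment invites the first reading.

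**Working it through.** **Inputs.** Means and SDs at week 0, at week 16 and for change come from Table 2. Table 2 prints no group sizes. For irritability, the means of integer scores fit AP-weekly n=15 and NP n=16; error df 33 = N - 4 gives N=37, hence UC n=6. Rows with 34 df fit 15/6/17.

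**Method.** Within-group covariance = (SD0² + SD16² - SDchange²)/2. For irritability:
- AP-weekly: (9.04² + 8.55² - 5.82²)/2 = 60.48
- UC: (5.38² + 6.97² - 4.65²)/2 = 27.95
- NP: (5.15² + 1.39² - 4.32²)/2 = 4.90

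Pooled slope b = (14×60.48 + 5×27.95 + 15×4.90)/(14×9.04² + 5×5.38² + 15×5.15²) = 1059.9/1686.7 = 0.63.

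**Reproducing the printed test.** The rebuilt ANCOVA gives F(2,33)=6.87, p=0.0032, against 6.89 and 0.003 printed. Rounding of the inputs allows 6.84 to 6.91. The 0.003 is printed as eta-squared but must be a p-value: partial eta-squared would be 2×6.89/(2×6.89 + 33) = 0.29.

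**Decomposition.** ANCOVA difference = (difference in change) + (1 - b) × (baseline gap), with 1 - b = 0.372.
- AP-NP: gap 11.33 - 2.31 = 9.02; change -1.27 - (-1.38) = 0.11; 0.11 + 0.372×9.02 = 0.11 + 3.35 = 3.46.
- NP-UC: gap 2.31 - 15.83 = -13.52; change -1.38 - 3.00 = -4.38; adding 0.372×(-13.52) = -5.02 gives -9.39 before rounding.

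**Precision.** Change: error mean square = (14×5.82² + 5×4.65² + 15×4.32²)/34 = 25.36, SE = √[25.36(1/n₁ + 1/n₂)], t(34)=2.03. ANCOVA: error mean square 19.07, SE = √[19.07(1/n₁ + 1/n₂ + gap²/1686.7)], t(33)=2.03.

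| Irritability | Change (95% CI), p | ANCOVA (95% CI), p |
|---|---|---|
| AP-NP | +0.11 (-3.57 to 3.79), 0.95 | +3.46 (-0.28 to 7.20), 0.07 |
| NP-UC | -4.38 (-9.28 to 0.52), 0.08 | -9.39 (-14.56 to -4.23), 0.0008 |

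**CBCL total** (b=0.72; rebuilt F 2.01, printed 2.02). AP-NP: -0.22 (p=0.97) as change, +10.40 (p=0.13) by ANCOVA. NP-UC: -3.04 (p=0.69) against -17.61 (p=0.06). The pattern is the same, but nothing reaches 0.05.

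**Adiposity rows**, NP-UC:

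| Row | Slope | Change | ANCOVA |
|---|---|---|---|
| Weight (kg) | 0.99 | -4.72 | -4.48 |
| DEXA % fat | 1.10 | -2.18 | -1.92 |
| Percent overweight | 1.04 | -8.52 | -8.94 |

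**Primary risk factors.** Table 2 has no week-16 values for DEXA total fat, PDFF or CIMT, so their slopes are unknown. Baseline gaps from Table 1:
- PDFF, NP vs UC: 4.72 - 12.01 = -7.29 points, or 0.85 of the combined SD of 8.54. At assumed slopes of 0.9 to 0.7 the extra term would be 0.7 to 2.2 points in size.
- CIMT, AP-weekly vs NP: 0.0451 - 0.0504 = -0.0053 cm, or 0.76 of the combined SD of 0.0070. The carotid ultrasound paragraph says the "intraclass correlation coefficients for IMT measurements at our laboratory are 0.91 and 0.88". If these stood in for the slope, the term would be 0.0005 to 0.0006 cm in size. They are observer reliabilities, so the slope over 16 weeks could be lower. At an assumed 0.7 the term is 0.0016 cm.

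**The case against.** The strongest reply is that neither estimator is assumption-free. ANCOVA assumes that children from either population with the same baseline would have the same expected week-16 value if treated alike. The change score assumes equal change in psychiatric and healthy children without the intervention. The documents can verify neither, so ANCOVA cannot simply be called biased and change correct. This stands, and it is why the two should be shown side by side.

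Irritability is also an unfavourable example. NP children sit near the floor (week-16 mean 0.94, SD 1.39). Dividing each covariance by SD0² gives slopes of 0.74 in AP-weekly, 0.97 in UC and 0.18 in NP, so the pooled 0.63 is partly a floor effect and not only measurement error or natural fluctuation. It should not be carried over to imaging outcomes. This stands too.

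A reader might infer three stronger things that the documents do not support.
- That the irritability result collapses because a one-way comparison of change gives F(2,34)=1.86, p=0.17. That omnibus test includes the randomised AP-weekly vs UC contrast, where ANCOVA belongs (-5.93, p=0.010 in the three-group model; -5.32, p=0.06 from those two arms alone). The 1.86 should not replace 6.89.
- That the extra term generally favours the Primary Hypothesis. It would for NP vs UC on PDFF and behaviour, but for weight and DEXA percent fat ANCOVA is slightly less favourable to weekly treatment than change is.
- That a primary result is wrong. No such error can be shown: the PDFF range and the larger CIMT figure rest on assumed slopes.

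**Conclusion.** The point holds in limited form. For two of the three named contrasts, the planned model does not estimate the stated target when the slope is below 1, and the plan has no check for this. On irritability the choice of method decides the reading. AP-weekly and NP children changed almost equally, yet the ANCOVA separates them by 3.46 points, of which 3.35 comes from the baseline gap. The NP-UC estimate roughly doubles and crosses 0.05. CBCL total behaves alike without reaching significance. On the adiposity rows checked, the two methods largely agree.

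For DEXA total fat, PDFF and CIMT the effect is unknown; the PDFF and CIMT baseline gaps are large enough that it needs checking.

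The figures rest on the inferred group sizes, supported by the close match to the printed F, and on a common slope that does not look common for irritability. This should be fixed, but it does not overturn any primary conclusion that the documents allow one to examine.

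**What to change.** Keep the ANCOVA for the randomised AP-weekly vs UC contrast. For AP-weekly vs NP and NP vs UC:
- report the difference in mean change with its 95% CI beside the ANCOVA estimate, for the three risk factors and for the behavioural scales;
- state the untestable assumption behind each estimate;
- do not claim a different response where the two disagree.

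In Table 2, label the group test as the baseline-adjusted comparison that it is, and print the group sizes.

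The cost is a few sentences in the Analytic approach and a re-run on existing data. Conclusions about the NP contrasts become somewhat more cautious.

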Understanding of Materials Scale: In order to determine the understanding of the scales and program presented, the therapist/research staff will complete an Understanding of Materials Scale after each session with both parent and child participants. This will allow the therapist and PI to periodically evaluate the general level of understanding and determine if changes to the protocol are needed.

Homework Quality Scale: Completion of homework assignments is a major component in the psychotherapy throughout this program, with the ability to impact the successful outcome of the treatment. The Homework Quality Scale will be completed by the therapist/PI after each session and will be used to assess the quality of homework in relation to the outcome of the therapy at the end of the study.

Working Alliance Inventory: The Working Alliance inventory measures the quality of the therapeutic relationship between the therapist and the patient (or youth and parent in this case). For the present study, both parent and child will be asked to anonymously fill out the "Client" version of the inventory and mail back in a self-addressed, stamped envelope provided to them at the 8 and 16 week sessions. The therapist will also fill out the Therapist version of the WAI at the same time points.

Modified TLP Therapist Fidelity Rating Checklist: This checklist includes items to assess therapist fidelity to the manualized therapy, and also includes therapist competency measures. This checklist has been used to monitor therapy fidelity in federally funded studies of both TLP and FBT behavioral weight loss programming.

DATA MANAGEMENT, SAFETY & ADVERSE EVENT REPORTING

Power: Our interest in conducting this study was to evaluate feasibility of delivering the weight loss intervention in antipsychotic (AP) treated versus nonpsychiatric (NP) overweight or obese youth, and to assess the effect of weight loss on metabolic measures of interest – CIMT/DEXA/PDDF in the AP-treated and NP active intervention groups as well as in a usual care (UC) reference group of obese youths. Comparisons of interest were between each of the two active treatment groups and UC, as well as between the two active intervention groups themselves (AP-treated vs. NP). Limited prior research in this area complicated power calculations for this pilot study.

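### The plan does not rest its treatment-effect conclusion on weekly BWL versus usual care in antipsychotic-treated youth, the only randomised comparison, and one permitted reading of the Primary Hypothesis can be met without it

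*Combined protocol and SAP*

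**What the plan says.** The synopsis presents the study as randomised ("Study Aims for this pilot randomized controlled trial"). The Specific Aims describe "antipsychotic (AP)-treated children randomized 2:1 to weekly BWL treatment or monthly diet and exercise education or usual care (UC), versus nonpsychiatric (NP"; the sentence continues by naming NP children as a further group who all receive weekly BWL. Randomisation is thus confined to the AP-treated children. The eligibility criteria bar NP children from having any Axis I diagnosis or any lifetime antipsychotic use.

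The Primary Hypothesis is that change in total fat and PDFF/IMT "will be more pronounced in the weekly weight loss intervention groups compared to the monthly Usual Care intervention". There are two weekly groups, AP and NP.

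The Analytic approach sets out a baseline-adjusted ANCOVA in which "the predictors are the baseline value of the risk factor and the study group (three level factor), with contrasts of interest listed above". On those contrasts it says: "Comparisons of interest were between each of the two active treatment groups and UC", and it adds the comparison of the two active groups with each other. The Power paragraph lists the same three. Neither ranks them or says which is randomised. The two paragraphs describe the control arm as "an obese usual care (UC) reference group" and "as well as in a usual care (UC) reference group of obese youths". Aims 1 to 3 do say that UC consists of randomised AP-treated youth, and Tables 1 and 2 label the arm as AP-treated.

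The power calculations are for the three groups together. The only difference in kilograms is for a non-randomised pair: "we estimated a difference between active treatment groups (AP-treated vs. NP) of 2 +/-3 kg loss".

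**The concern.** A trial that calls itself randomised should draw its treatment-effect conclusion from the randomised comparison. Here AP-BWL vs UC is one of three equal contrasts, and the hypothesis is worded to take in the NP group.

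NP vs UC differs in three things at once: the intervention, psychiatric diagnosis and antipsychotic exposure. The last two are fixed by eligibility with no overlap between groups. Neither baseline adjustment nor the planned age and gender covariates, entered one at a time, can separate them from treatment.

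At stake is a positive result that comes from the response of healthy, unmedicated children and is then read as benefit in antipsychotic-treated youth. Table 2 prints change by arm and a three-group F, but no contrast and no confidence interval, so for the measures it covers a reader cannot see directly what the randomised comparison shows.

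**Working it through.** **1. What the stated power refers to.** Omnibus F test, 20 per group, noncentrality λ = f² × 60, df 2 and 57:
- CIMT: 0.16² × 60 = 1.54, power 0.174 (stated 0.17)
- Hepatic triglyceride: 0.49² × 60 = 14.41, power 0.922 (stated 0.92)
- DEXA total fat: 0.53² × 60 = 16.85, power 0.956 (stated 0.96)

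All three are reproduced, so the stated power belongs to a 2-df test that includes NP and not to the randomised contrast.

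**2. Can the hypothesis be met with no benefit in AP children?** Simulation with AP-BWL equal to UC and an NP effect of d = 2/3 = 0.67. The 2 and 3 kg come from the Power section; applying them here is an assumption. Two-sided 0.05, 100,000 runs. Share of trials significant (for the contrasts, in favour of BWL):

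| n (AP/UC/NP) | AP-BWL vs UC | NP vs UC | Weekly groups pooled vs UC | Omnibus |
|---|---|---|---|---|
| 20/20/20 | 2.5% | 54% | 22% | 55% |
| 15/6/17 | 2.5% | 28% | 12% | 40% |

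This shows what is possible, not what happened.

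**3. Illustration from Table 2.** Arm sizes are inferred. F[2,34] with one covariate gives N = 34 + 3 + 1 = 38. For UC, the time-effect η² = t²/(t² + n - 1) with t² = n × (mean change/SD)²; n = 6 gives 0.558 for weight, 0.685 for LDL and 0.590 for triglycerides (printed 0.56, 0.69, 0.59). The other arms fit 15 and 17.

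For each arm, cov = (s0² + s16² - sΔ²)/2. Pooling with weights n - 1 gives Sxx, Sxy and Syy. Then slope b = Sxy/Sxx, MSE = (Syy - Sxy²/Sxx)/34, contrast = Σw(ȳ - b·x̄), and SE = √{MSE[Σw²/n + (Σw·x̄)²/Sxx]}.

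Weight: Sxx = 25,501.0, Sxy = 25,189.7, Syy = 25,330.1, b = 0.9878, MSE = 13.17. Rebuilt F = 3.38 (printed 3.37).
- Randomised AP-BWL vs UC: (77.92 - 70.98) - 0.9878 × (78.04 - 68.56) = -2.42. SE = √[13.17 × (1/15 + 1/6 + 9.48²/25,501)] = 1.77. 95% CI -6.0 to 1.2, p = 0.18.
- NP vs UC: (86.19 - 70.98) - 0.9878 × (88.49 - 68.56) = -4.48, SE 1.78. 95% CI -8.1 to -0.9, p = 0.017.
- Equal-weight average of the weekly groups vs UC: -3.5, p = 0.044.

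Percent overweight (rebuilt F 3.28, printed 3.29): randomised -5.1 (-12.4 to 2.2), p = 0.16; NP vs UC -8.9 (-16.2 to -1.7), p = 0.017; weekly average -7.0, p = 0.042.

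Fitting AP children only, the randomised p values are 0.11 (weight) and 0.15 (percent overweight).

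**4. Sensitivity.** Over seven splits of N = 38 with UC at 5 to 7:
- Weight: NP vs UC p = 0.012 to 0.025; randomised p = 0.15 to 0.21.
- Percent overweight: 0.014 to 0.023 against 0.15 to 0.19.
- The weekly average is less stable, p = 0.03 to 0.06.

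**5. Rows that do not follow the pattern.** NP vs UC has p < 0.05 in 4 of 15 rows (weight, percent overweight, HDL, irritability) and the randomised contrast in 2 (HDL, irritability). For HDL the two agree: +6.0 (p = 0.042) randomised and +5.9 (p = 0.045) for NP vs UC. For DEXA % fat neither is significant (p = 0.53 and 0.12).

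**The case against.** The strongest reply is that nothing is missing. AP-BWL vs UC is a listed contrast, the ANCOVA estimates it directly, and the NP group is a deliberate comparator in a pilot whose stated interests include feasibility and change in all three groups. This stands, and limits the point to ranking, labelling and interpretation.

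Second, a reader might infer from the Power and Analytic approach paragraphs that the plan never says who the UC children are. The documents do not support that: the Aims identify them as randomised AP-treated youth and the tables label them AP-treated. Those two paragraphs simply do not repeat it.

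Third, the contrast wording takes each active group against UC. Read with the hypothesis, this allows the view that both weekly groups must beat UC, in which case NP vs UC alone would not suffice. That is a fair reading, but the text does not state it. Nor is a pooled weekly contrast in the Analytic approach; it is only one way to read the hypothesis.

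Fourth, no passage draws a treatment-effect conclusion for AP youth from NP vs UC, and Table 2 covers additional measures only. How contrasts were reported for the aim outcomes cannot be judged from these documents. Both limits stand. They bear on whether harm has occurred, not on the gap in the plan.

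**Conclusion.** The point holds and should be fixed. The plan lists the only randomised comparison without rank beside two non-randomised ones, and its Primary Hypothesis does not say whether each, both or a pooled comparison must succeed. Because NP vs UC is confounded by design, one permitted reading lets the hypothesis be met with no benefit in the randomised children. This rests on the text alone.

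The Table 2 figures are illustration. They depend on inferred arm sizes, about 6 UC completers and nominal p values; p = 0.017 narrowly misses a Bonferroni threshold for three contrasts (0.05/3 = 0.0167). In two rows, weight and percent overweight, the answer at 0.05 depends on which comparison is taken as the hypothesis.

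Three stronger inferences are not supported:
- That BWL fails in AP-treated youth: a weight interval of -6.0 to 1.2 kg excludes neither a useful benefit nor none.
- That NP children respond better than AP children: NP vs AP-BWL is itself non-significant (weight p = 0.13, percent overweight p = 0.17).
- That an aim outcome is affected: Table 2 holds no change data for DEXA total fat, PDFF or CIMT.

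**What to change.** In the Analytic approach, add wording to this effect:

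> For each outcome the treatment-effect conclusion rests on AP-BWL vs AP-UC, the randomised contrast, reported with its 95% CI. NP vs AP-BWL is a planned, non-randomised comparison of response between populations. NP vs UC is also non-randomised. No treatment-effect conclusion is drawn from NP vs UC or from the weekly groups combined.

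Leave the Primary Hypothesis as worded and add beneath it that its efficacy reading rests on AP-BWL vs AP-UC. Report the three contrasts with 95% CIs, including beside each F in Table 2. Disclose that this ordering was set after the data were tabulated.

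An ANCOVA in AP-treated participants only is an optional check. It has 18 error df instead of 34, and its SE falls in some rows (weight 1.77 to 1.41) and rises in others (HDL 2.84 to 3.11).

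The cost is wording and a re-run on existing data; the planned AP vs NP comparison is kept. The real price is precision: the treatment-effect estimate rests on about 6 UC completers, with a weight interval about 7 kg wide (1.2 + 6.0 = 7.2).
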